#### **3.6.1 *Withdrawal of Consent***

Subjects who request to discontinue study treatment will remain in the study and must continue to be followed for protocol specified follow-up procedures. The only exception to this is when a subject specifically withdraws consent for any further contact with him/her or persons previously authorized by subject to provide this information. Subjects should notify the investigator of the decision to withdraw consent from future follow-up **in writing**, whenever possible. The withdrawal of consent should be explained in detail in the medical records by the investigator, as to whether the withdrawal is from further treatment with study drug only or also from study procedures and/or post treatment study follow-up, and entered on the appropriate CRF page. Since vital status (whether the subject is alive or dead) is being measured, publicly available information should be used to determine vital status only as appropriately directed in accordance with local law.

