## 8.2 Populations for Analyses

- The primary endpoint will be initially assessed on the ITT population in each treatment group. The ITT population will consist of all randomized and transplanted subjects treated with at least one dose of Thymoglobulin and one dose of study treatment, either belatacept or TAC, and will be included in the safety and efficacy analysis data sets. In these analyses, CSBPARs occurring after discontinuation from assigned therapy will be counted in the treatment arm to which the subject was originally randomized.
- Additionally, for CSBPAR, a sensitivity analysis will be performed with right censoring at the time of discontinuation from the assigned therapy.
- An as-treated analysis will be based on the treatment regimen received. Analysis of treatment differences in the rates of CSBPAR will only include those subjects who remain on their original therapy from the beginning, through the designated analysis time point(s) (e.g., the Months 6, 12 and 24 study visits) for these above mentioned analyses. Treatment differences in the rates of CSBPAR will also be performed using a per protocol efficacy dataset.
  - This is defined as the set of all data derived from that subset of subjects once treated, are followed up consistently with all study criteria to the extent that no relevant protocol deviations have been identified.

The primary analysis will be done on the ITT population and the sensitivity analyses on the primary endpoints will be done in the As Treated, as well as the Per Protocol population.

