7.2 General Methods

All analyses of efficacy and safety endpoints will be summarized descriptively by the two treatment groups. No statistical tests will be performed.

Randomization to the study will be stratified by site only. Any within-treatment confidence interval (CI) for the proportion analyses will be computed using normal approximation, if the number of the events in that treatment group is at least 5. Otherwise, a CI calculated using an exact method will be provided. Any between-treatment CI for the proportion difference analyses will also be computed using normal approximation, if the number of the events in each individual treatment group is at least 5. Otherwise, a CI using an exact method will be provided.

For time to event analyses, if a patient does not experience an event, the censoring will be done at the last follow-up date if the subject discontinues prematurely; otherwise, censoring will be

done at the last dose date if the subject completed the 24 month-treatment period, unless specified otherwise.

The following table provides an overview of the primary and key secondary analyses to be performed.

Table 7.2-1: Overview of Primary and Key Secondary Analyses

Measure of Interest	Analysis Method
Proportion of subjects who experience a CSBPAR at 6, 12 and 24 months post-transplant	Point estimate of the proportion and 95% CI [*] within each treatment group at 6 months.
Difference in the incidence of CSBPAR between arms, at 6, 12 and 24 months post-transplant	Point estimate and 95% CI [†] for the difference between the two arms
Time to first CSBPAR	Kaplan-Meier (KM) estimates of survival functions. Hazard Ratio and 95% CI [§]
Proportion of Subjects who survive with a functioning graft at 24 months post-transplant	Point estimate of the proportion and 95% CI [*] within each treatment group at 24 months (to be produced if there are at least 5 subjects across treatment groups who died or experienced graft loss)
Time to death or graft loss	KM estimate of subject and graft survival Hazard Ratio and 95%CI [§] (to be produced if there are at least 5 subjects across treatment groups who died or experienced graft loss)

* Confidence Interval Formula: Exact (Clopper-Pearson)

† Confidence Interval Method: Score (Wilson)

§ Using Cox Proportional Hazard model

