7.6.1 Primary Endpoints

7.6.1.1 Acute Rejection

Rates of acute rejection will be summarized by treatment group at Months 6, 12 and 24 using point estimates of the proportion of subjects experiencing at least one CSBPAR, and the corresponding 95% CIs. Two-sided 95% CIs will also be generated for the difference between the two treatment regimens. Descriptive statistics will be provided for the percentages of subjects with CSBPAR in each treatment group, including those for severity grade and treatment received (corticosteroids, lymphocyte depleting agents, renal replacement therapy, plasmapheresis, IVIg, rituximab). All grades of acute rejection, excluding those assessed by the pathologist as "borderline changes" (biopsy findings "suspicious" for acute cellular rejection per the Banff criteria), will be included in the analysis of the primary and relevant secondary endpoints for acute rejection. Sensitivity analyses will be performed, including acute rejections assessed by the pathologist as 'borderline changes' (biopsy findings "suspicious" for acute cellular rejection per the Banff criteria).

In addition, Kaplan-Meier (KM) cumulative event rates will also be performed by treatment groups and the corresponding hazard ratio will be calculated using cox proportional hazard model for the whole study treatment period (i.e. 24 months).

A corresponding listing including all suspected acute rejection events, regardless of when they occurred, will be provided. All events occurring more than 56 days since last dose date will be flagged.

An additional listing will be produced including subjects who post-CSBPAR, are reported to have developed infection or malignancy.

Sensitivity analyses

Sensitivity analyses will be performed on the PP population as well as on the AT population for the primary analysis, if there are in either treatment group at least 10% of subjects with a protocol deviation or subjects for which the as-randomized treatment group is different for the as-treated treatment group, respectively. The table below is a summary of the analysis along with the populations it will be performed in.

Table 7.6.1.1-1: Overview of Sensitivity Analysis

Measure of Interest	Analysis Method	Sensitivity Analysis Population
Proportion of subjects who experience a CSBPAR at 6, 12 and 24 months post-transplant	Point estimate of the proportion and 95% CI* within each treatment group at 6 months	AT and PP

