8.3 Missing Data Handling

The following conventions will be followed while handling missing data. Only the relevant endpoints along with the specifics of the convention are included in this section.

Subject Survival and Graft Survival

Any subject (either randomized to belatacept or CNI) with unknown subject and graft survival status at Month 12 or Month 24, that is, whose last known follow-up date occurred prior to Day 334 or Day 698, respectively, will be considered as having experienced an event of graft loss or death, if at least one of the following criteria have been met during their documented period of follow-up post-randomization:

- Subject experienced at least one episode of BPAR at the time of, or prior to the last follow-up date.
- Subject was diagnosed as having PTLD at the time of, or prior to the last follow-up date.
- Subject's reason for discontinuation of study medication was lack of efficacy.
- A diagnosis of biopsy confirmed Polyomavirus associated nephropathy was reported as an adverse event before discontinuation.
- Subject's last calculated GFR (4-variable MDRD equation) was $< 15\text{mL}/\text{min}/1.73\text{m}^2$.

The remaining subjects with unknown patient and/or graft survival status at Months 12 or 24 (those who do not meet any of the above criteria) will be considered missing and not be included in the analyses or listing of the death and graft loss. For example, a patient with unknown status of the graft function and patient survival, and with no records of the above mentioned criteria, will not be considered in the numerator or denominator, while computing the percentage of death or graft loss.

Acute Rejection

Any acute rejection-free subject who is not followed-up through the entire event-counting period due to any reason will be considered as having no acute rejection during that period.

Renal Function

Missing cGFR values due to death or graft loss will be imputed with value of 0 and all other missing values will remain missing.

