8.4 Day Ranges for Analysis Time Points

Subjects do not always adhere strictly to the visit schedule timing in the protocol. Therefore the designation of the visits/months during the study will be based on the day of evaluation relative to day 1 of the trial (first dose date = study day 1) rather than the nominal visit/month recorded in the case report form (CRF).

The following rules apply to the derived visits depending on the specific endpoint. All endpoints analyzed over time will follow the analysis windowing specified in Table 8.4-1.

Table 8.4-1: Day Ranges for Analysis Time Points

At Month	Target Day	Day Range
1	28	1-56
3	84	57-112
6	168	141-196
9	252	225-280
12	364	337-392
15	448	421-476
18	532	505-560
21	616	589-644
24	728	701-756

Note: If a subject has more than one measurement recorded within the window for that time point, the measurement closest to the target day for that time point will be used. In any case in which both observations are equidistant from the target day, the later measurement will be used.

If data are collected at Month 2 (Week 8) then the day ranges are the following:

At Month	Target Day	Day Range
1	28	1-42
2	56	43-70
3	84	71-112

At Month	Target Day	Day Range
...		

In addition, the analyses for subject and graft survival, acute rejection related endpoints, NODAT and adverse events will follow the windowing below:

- Month 6: Defined as Day 1 to Day 168.
- Month 12: Defined as Day 1 to Day 364.
- Month 24: Defined as Day 1 to Day 728.

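### Subjects lost before the end of the counting period are scored as free of acute rejection; no Month 6 Kaplan-Meier estimate with CI is named, and no analysis varies their outcome

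*SAP*

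**What the plan says.** **The rule.** Under acute rejection, SAP 8.3 reads: "Any acute rejection-free subject who is not followed-up through the entire event-counting period due to any reason will be considered as having no acute rejection" for that period. SAP 8.4 sets the primary window: "Month 6: Defined as Day 1 to Day 168". Months 12 and 24 run to Days 364 and 728. SAP 7.6.1.1 makes the main summary the proportion per group with at least one CSBPAR, with a 95% CI. A lost subject with no recorded rejection thus stays in the denominator as a non-event.

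**Time-to-event analyses kept.** SAP 7.6.1.1 adds that "Kaplan-Meier (KM) cumulative event rates will also be performed by treatment groups". For subjects without an event, SAP 7.2 says "the censoring will be done at the last follow-up date if the subject discontinues prematurely". The hazard ratio covers 24 months, and the Table 7.2-1 footnote ties the CI in the time-to-event row to the Cox model. SAP 7.6.2.2 keeps a composite of CSBPAR, death or graft loss. It has proportions at Months 12 and 24 and a time-to-event analysis, and is run only if there is at least one CSBPAR and at least one death or graft loss.

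**Follow-up after stopping treatment.** Under Protocol 3.6.1, subjects who stop treatment stay in the study and "must continue to be followed for protocol specified follow-up procedures". Under Protocol 8.2, "CSBPARs occurring after discontinuation from assigned therapy will be counted in the treatment arm to which the subject was originally randomized". SAP 7.6.1.1 adds: "A corresponding listing including all suspected acute rejection events, regardless of when they occurred, will be provided".

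**Analysis dropped.** Protocol 8.2 says "a sensitivity analysis will be performed with right censoring at the time of discontinuation from the assigned therapy". SAP 7.1, item 3(d), withdraws this.

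**Analysis set.** SAP 6.2 limits ITT to subjects randomized, transplanted and dosed with Thymoglobulin and with belatacept or tacrolimus. SAP 7.4.2 equates ITT with everyone randomized. SAP 7.4.1 wants randomized but untreated subjects listed, yet assigns its outputs to the ITT set.

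**The concern.** The rule works in one direction. A rejection that occurs after contact ends but inside the window is scored as none, and nothing in the rule can raise the rate. The research hypothesis is that rejection rates will be acceptable, so the error favours the hoped-for conclusion.

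Events are expected to be so few that one missed rejection doubles an observed rate. Detection depends on clinical suspicion, because Protocol 5.3.7 does not permit surveillance biopsies; a subject out of contact is unlikely to be diagnosed within the study.

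The same SAP section handles unknown survival status differently. Some unknowns become events after warning signs such as biopsy-proven rejection, and the rest leave the calculation. For rejection, every unknown is taken as the favourable outcome, with no reason given.

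The remaining sensitivity analyses do not test this. Including borderline changes alters the case definition. The per-protocol and as-treated analyses alter the population, and only if a 10% trigger is met.

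The analysis-set wording is a smaller, separate matter: readers may take the ITT set to be everyone randomized, which it is not.

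**Working it through.** **Inputs.** SAP Section 5 gives n = 35 per arm and assumed rates of 3.8% (belatacept + everolimus) and 3% (tacrolimus + MMF). The window is 168 days (SAP 8.4). Single-arm intervals are Clopper-Pearson throughout, as in the Table 7.2-1 footnote, although the text of SAP 7.2 would switch to a normal approximation at five or more events. Neither document gives a loss rate, so every loss figure below is an assumption.

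**1. The plan's own figures.**
- Expected events: 35 × 0.038 = 1.33 and 35 × 0.03 = 1.05.
- Clopper-Pearson at these values: 0.21% to 16.37% and 0.09% to 15.14%, matching the stated 0.2-16.4% and 0.1-15.1%.
- Wilson-score (Newcombe) interval for the difference, 35 per arm: -13.17% to 11.32%, matching SAP Table 5-1.

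**2. Direction.** Let E be recorded events and r the unseen rejections among lost subjects. The plan reports E/35; the true figure is (E + r)/35. Since r cannot be negative, the shortfall is r/35, or 2.9 points for each unseen rejection.

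**3. Loss unrelated to rejection.** Assume a constant hazard h = -ln(1 - 0.038) = 0.03874 over the window and loss times spread evenly. The chance that a lost subject's rejection is recorded before loss is 1 - (1 - e^-h)/h = 1 - 0.038/0.03874 = 0.0191. With a fraction d lost, the reported rate is (1 - d) × 0.038 + d × 0.0191.
- d = 10%: 0.0342 + 0.0019 = 3.61%.
- d = 20%: 0.0304 + 0.0038 = 3.42%.
- If rejection is still observed for 56 days after discontinuation: 3.72% and 3.63%.

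The shortfall is 0.1 to 0.4 points, against a planned interval about 16 points wide (16.4 - 0.2).

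**4. Loss related to rejection.**
- 20% lost, with twice the hazard in those lost: true 4.53%, reported 3.80%. With three times the hazard: true 5.23%, reported 4.16%.
- In whole subjects: 1/35 = 2.9% (0.1-14.9); with one unseen rejection, 2/35 = 5.7% (0.7-19.2).
- Difference between arms: 1/35 v 1/35 is 0 (-11.9 to 11.9); 2/35 v 1/35 is 2.9 points (-9.5 to 16.0).
- Extreme bound, one recorded event and every lost subject rejecting: 2 lost, 3/35 = 8.6% (1.8-23.1); 4 lost, 5/35 = 14.3% (4.8-30.3); 7 lost, 8/35 = 22.9% (10.4-40.1).

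**5. What KM adds.** With one event occurring after 2, 4 or 7 losses, KM gives 1/33 = 3.0%, 1/31 = 3.2% or 1/28 = 3.6%. It adjusts the risk set but assumes that lost subjects carry the same risk as those who stay, so it cannot reveal the situation in step 4. It also overstates cumulative incidence if deaths are censored. If the two subjects who leave first have died, KM still gives 1/33 = 3.0%, whereas the cumulative incidence with death as a competing event is (33/35) × (1/33) = 1/35 = 2.9%.

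**6. Analysis set.** A set that requires dosing (SAP 6.2) cannot be everyone randomized (SAP 7.4.2), nor can it supply a listing of untreated subjects (SAP 7.4.1).

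**The case against.** The strongest reply is that the plan already covers much of this. A reader might infer that rejections are ignored once treatment stops. The documents say otherwise: such subjects remain in follow-up and their rejections are counted and listed. Protocol 3.6 does name only subject and graft survival as the data collected through Month 24, but the rule bites mainly on subjects whose follow-up itself ends.

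A reader might also infer that time-to-event handling is absent. It is not: a Month 6 value lies on the planned KM curve, and SAP 7.1, item 1, mentions analyses at 6 or 12 months. The gap is a named Month 6 estimate with a CI, and part of SAP Section 8 is blacked out, so even that absence is established only for the readable text. The composite covers dropout through death or graft loss when its condition is met, though its proportions omit Month 6. Discontinuations with reasons by arm (SAP 7.4.1) and a listing of unknown survival and graft status (SAP 7.6.2.1) are also planned.

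Next, incomplete follow-up includes death. For a subject who dies without rejection, no rejection is the true status. A worst-case row over everyone scored under SAP 8.3 would count such deaths as rejections. This objection stands, and the fix allows for it.

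Finally, dropping the analysis censored at treatment discontinuation might look like the loss of the safeguard. It is not: that analysis concerns stopping therapy rather than losing follow-up, would discard observed off-therapy rejections, and also assumes non-informative censoring. SAP 7.1 discloses the change and relates its modifications to the smaller sample. There is no need to restore it.

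**Conclusion.** The concern holds as a gap in specification. By rule, loss of contact or withdrawal of consent can only lower the crude CSBPAR proportions or leave them unchanged, and no readable analysis varies the outcome of lost subjects.

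Under non-informative loss the effect is 0.1 to 0.4 points at a true 3.8%, assuming 10-20% loss, a constant hazard and evenly spread loss times. That is minor in a descriptive study of this size. If loss is related to rejection, a single unseen event moves 2.9% to 5.7%.

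A reader might take 14.3% or 22.9% as the likely error. The documents do not support that: they give no loss rate, and those figures require every lost subject to have rejected. They are extreme bounds only.

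The ITT contradiction is certain from the text but minor. A reader might infer that untreated subjects are meant to be hidden. SAP 7.4.1 explicitly asks for them, so the population sentence there is more likely misplaced than intended.

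**What to change.** - **Estimate.** Beside the crude proportion, report cumulative CSBPAR with 95% CIs at Months 6, 12 and 24 from the planned time-to-event analysis. Censor at last follow-up and treat death and graft loss as competing events, or also give the composite at Month 6. If an arm has no events, use the exact interval (0/35: 0 to 10.0%).
- **Count and bound.** Report per arm how many subjects are scored as non-events under SAP 8.3, split into death, graft loss, and loss of contact or withdrawal. Add a row that scores only the last group as events, labelled as an extreme bound. If that group is empty, the table shows it and the primary result is strengthened.
- **Analysis set.** Label the set modified ITT, correct the description in SAP 7.4.2, and base the SAP 7.4.1 disposition and its listing of untreated subjects on all enrolled and randomized subjects.

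The cost is SAP wording and a few table rows, and the reported rates may be slightly less favourable. The censoring date is one that SAP 7.2 already uses.

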8.4 Day Ranges for Analysis Time Points

Subjects do not always adhere strictly to the visit schedule timing in the protocol. Therefore the designation of the visits/months during the study will be based on the day of evaluation relative to day 1 of the trial (first dose date = study day 1) rather than the nominal visit/month recorded in the case report form (CRF).

The following rules apply to the derived visits depending on the specific endpoint. All endpoints analyzed over time will follow the analysis windowing specified in Table 8.4-1.

Table 8.4-1: Day Ranges for Analysis Time Points

At Month	Target Day	Day Range
1	28	1-56
3	84	57-112
6	168	141-196
9	252	225-280
12	364	337-392
15	448	421-476
18	532	505-560
21	616	589-644
24	728	701-756

Note: If a subject has more than one measurement recorded within the window for that time point, the measurement closest to the target day for that time point will be used. In any case in which both observations are equidistant from the target day, the later measurement will be used.

If data are collected at Month 2 (Week 8) then the day ranges are the following:

At Month	Target Day	Day Range
1	28	1-42
2	56	43-70
3	84	71-112

At Month	Target Day	Day Range
...		

In addition, the analyses for subject and graft survival, acute rejection related endpoints, NODAT and adverse events will follow the windowing below:

- Month 6: Defined as Day 1 to Day 168.
- Month 12: Defined as Day 1 to Day 364.
- Month 24: Defined as Day 1 to Day 728.

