**Table 5.1-3: Procedural Outline - Year 2 through End of Treatment (IM103177)**

Procedure			M 15		M 18		M 21		M 24/ET a		FU	Notes		
	W 56	W 60	W 64	W 68	W 72	W 76	W 80	W 84	W 88	W 92	W 96	W 100	W 104	W 8/12/24
LOCAL LABS														
Serum Creatinine			X			X			X				X	
Pregnancy Test	X*	X*	X	X*	X*	X	X*	X*	X	X*	X*	X*	X	X**
Everolimus Trough						X							X	
Tacrolimus Trough						X							X	
CENTRAL LABS														
Urine collection						X							X	
Hematology w/diff						X							X	
Hemoglobin A1c													X	

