### **5.3.2 Visit Windows**

For the purpose of this study, "Week" refers to the end of treatment week (eg. Week 4 = Day 29, Week 8 = Day 57, etc). Visit windows are provided for site staff and subject convenience. After Day 1, it is recommended, whenever possible, that visits be scheduled Monday through Thursday as permitted by the visit window, to allow for the timely shipment of samples to the central laboratory. See [Table 5.3.2-1](#):

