**Table 5.3.2-1: Visit windows for study procedures and infusion (when applicable)**

Visit/Infusion	Visit Window
Day 1	Day of Transplant; see Section 4.3 for details regarding the timing of the initial dose relative to kidney transplantation and temporal sequence of study drugs.
Week 1 (Day 7)	Target date $\pm$ 1 day
Week 2 (Day 15)	Target date $\pm$ 2 days
Week 4 - Month 6	Target date $\pm$ 3 days
Month 7 - Month 24	Target date $\pm$ 5 days
Early Termination (ET)	Within 14 days after discontinuation of study drug. If the visit cannot be completed within the window (eg, due to hospitalization, etc), the visit should be completed as soon as possible thereafter.
Follow-up 8, 12, 24 weeks	Target date from date of last dose of study drug $\pm$ 5 days

Phone visits for subject randomized to receive TAC may commence after the Month 6 visit (excluding visits for months 9, 12, 15, 18, 21, and 24, which should be completed in the office). Subjects will be contacted to assess for AEs and concomitant medications. Each of these visits should occur within the prescribed visit window.

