8.2 Analysis Period of Interest

All analyses will be produced for the 24 month-treatment period, unless specified otherwise in the sections above. For these analyses focusing at month 6 and month 12, the analyses conventions in [Section 8.4](#) will be followed.

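### The Month 24 NODAT count closes at Day 728, one day before the target day of the Week 104 visit that carries the only visible Year 2 HbA1c

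*SAP*

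**What the plan says.** SAP 8.4 assigns results by actual study day, "relative to day 1 of the trial (first dose date = study day 1", and not by the visit name on the CRF. It then gives two sets of windows.

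- Measured values: "All endpoints analyzed over time will follow the analysis windowing specified in Table 8.4-1". That table gives Month 24 a range of Days 701 to 756.
- Cumulative events: subject and graft survival, "acute rejection related endpoints, NODAT and adverse events will follow the windowing below". The last of those windows is "Month 24: Defined as Day 1 to Day 728".

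SAP 8.2 adds a general statement: "All analyses will be produced for the 24 month-treatment period, unless specified otherwise in the sections above". It then refers only the Month 6 and Month 12 analyses to 8.4.

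In protocol 5.3.2 a week "refers to the end of treatment week (eg. Week 4 = Day 29, Week 8 = Day 57, etc". Protocol Table 5.3.2-1 allows ±5 days for "Month 7 - Month 24". In the visible part of protocol Table 5.1-3, the row "Hemoglobin A1c" has one mark, at Week 104/ET.

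Protocol 5.3.15 makes HbA1c of 6.5% or more a NODAT criterion, alongside glucose criteria and at least 30 days of anti-diabetic medication. NODAT incidence at 6, 12 and 24 months is a listed secondary endpoint, with a 95% CI in each group (SAP 7.6.2.5).

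**The concern.** The SAP numbers months as 7 × weeks. The protocol numbers visits as 7 × weeks + 1. For most endpoints a one-day offset is harmless. For NODAT at Month 24 it matters more, because the visible Year 2 HbA1c is taken at the visit that falls on the far side of the cut.

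The same offset occurs at Months 6 and 12, but the windows are cumulative, so a case missed there enters the next one. Month 24 has no later window. A case first revealed by an on-time final HbA1c would be left out of the incidence table by a stated rule, although the sample was taken as the protocol asks. What is at stake is whether the Month 24 NODAT proportion includes the visit meant to inform it.

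**Working it through.** **Inputs**
- Month 24 cut for NODAT: Day 728 (SAP 8.4).
- Week-to-day examples: Week 2 = Day 15, Week 4 = Day 29, Week 8 = Day 57 (protocol 5.3.2 and Table 5.3.2-1).
- Visit window at Week 104: ±5 days (protocol Table 5.3.2-1).
- Month 24 range for measured values: Days 701 to 756 (SAP Table 8.4-1).
- Subjects per arm: 35.

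**The SAP's figures reproduce.** 24 × 7 = 168, 52 × 7 = 364 and 104 × 7 = 728.

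**The protocol's rule.** 7 × 2 + 1 = 15, 7 × 4 + 1 = 29 and 7 × 8 + 1 = 57, so Day = 7 × week + 1. Week 104 is then 7 × 104 + 1 = Day 729, and ±5 gives Days 724 to 734. The protocol does not print a day for Week 104. Week 1 = Day 7 is an exception to the rule.

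**Permitted Week 104 visit days after Day 728**

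| Reading | Week 104 in SAP days | Permitted range | After Day 728 |
|---|---|---|---|
| Day 1 = transplant and first Thymoglobulin | 729 | 724–734 | 6 of 11 |
| Day 1 = first belatacept or tacrolimus, given on Day 2 | 728 | 723–733 | 5 of 11 |
| Day 1 = first tacrolimus, given on Day 7 | 723 | 718–728 | 0 of 11 |

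Keeping the transplant-day anchor but counting Week 104 as 7 × 104 = Day 728, in the way Week 1 is Day 7, also gives 5 of 11. In every row the whole permitted range lies inside Days 701 to 756.

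**Earlier time points, transplant-day anchor.** Week 24 = Day 169 ±3, so 4 of 7 days fall after Day 168. Week 52 = Day 365 ±5, so 6 of 11 fall after Day 364. Both carry forward to the next window.

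**Size of one omitted case.** 1/35 = 2.9 percentage points. With Clopper-Pearson limits, 0/35 gives 0% (95% CI 0 to 10.0%) and 1/35 gives 2.9% (0.1 to 14.9%). If 20% to 40% of an arm were already diabetic and left out of the denominator (my assumption; 28 to 21 subjects), one case is 1/28 = 3.6 to 1/21 = 4.8 points.

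**Whether the primary endpoint needs the same change.** Under a constant hazard, adding Days 169 to 172 to the Month 6 rejection window adds 35 × 3% × 4/168 = 0.025 events in the tacrolimus arm and 35 × 3.8% × 4/168 = 0.032 in the belatacept arm. It does not.

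**The case against.** The best defence is that Day 728 is the SAP's consistent meaning of 24 months. It is the target day in Table 8.4-1 and the cut for survival, rejection and adverse events. The exposure bands in SAP 7.5 also place Day 729 beyond 24 months. Closing a cumulative incidence on a fixed day is ordinary practice. That stands for the other endpoints. It does not explain why the NODAT count should stop just short of the scheduled test. SAP 8.2 leaves some room to include the visit, but it gives no end day, while 8.4 gives one expressly.

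Second, Day 729 depends on the anchor. SAP 6.2 names Thymoglobulin separately from study treatment, which it limits to belatacept or tacrolimus, so the first dose could be read as either of those. Protocol 4.1.1 lists Thymoglobulin as an investigational product, and Table 5.1-4 labels the day of transplant as the first dosing day; I find that reading better supported. The objection still stands as a reason to show the range and to define Day 1.

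Third, the affected group is narrow.
- Medication or glucose may establish NODAT earlier, and the Year 2 chemistry schedule is not visible.
- Subjects who stop early have HbA1c at the ET visit, usually well before Day 728, so mainly completers are exposed.
- Absent unequivocal hyperglycemia, protocol 5.3.15 asks for a repeat test to confirm. No visible scheduled visit after Week 104 provides one, and the SAP does not say which test dates the event.

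All of this stands and keeps the point minor.

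A reader might also infer that two Month 24 tables would contradict each other, because the same HbA1c enters the Month 24 HbA1c summary. The documents do not support that: the planned HbA1c output is means and changes from baseline, with no count of values at or above 6.5%.

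**Conclusion.** The concern holds as a minor one. Under the stated rule, a NODAT case first shown at an on-time or late Week 104 visit could be left out of the Month 24 incidence and its CI. On the transplant-day anchor this covers 6 of 11 permitted visit days; on the other anchors shown it is 5 or 0 of 11. Each omitted case is worth 2.9 points at n=35.

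Three stronger inferences should be resisted.
- The 6 of 11 is a share of permitted days, not of cases. The number of cases affected cannot be derived from the documents and may be zero.
- The case is not lost from the record. Protocol 5.3.15 requires NODAT to be reported as an adverse event, and SAP 7.7.1.2 bases the listings on all data to database lock.
- No bias between arms is shown. On the transplant-day anchor the cut is the same in both arms, and the study is descriptive with no statistical tests. On a belatacept or tacrolimus anchor the cut could fall differently relative to the visit, which is one more reason to state the anchor.

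The conclusion rests on the 7 × week + 1 rule extending to Week 104, and on HbA1c having no other Year 2 mark in text that is not visible.

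**What to change.** In SAP 8.4, for NODAT at Month 24 only:

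- Close the counting period at the later of Day 728 and the subject's Week 104 visit. Accept visits through Day 734, or at most Day 756, the upper limit of Table 8.4-1. Moving the cut to Day 729 would not be enough: 5 of 11 permitted days (730 to 734) would still fall outside.
- Apply this to every NODAT criterion, medication as well as laboratory, so that late cases are not admitted by one route and refused by another.
- Date a laboratory case at its first qualifying result. A repeat test confirms the case but does not set its date.

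Separately, state which drug's first dose defines study Day 1. This is a clarification for every endpoint in 8.4, not for NODAT alone.

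Leave the Month 6 and Month 12 NODAT windows unchanged, and likewise the windows for rejection, survival and adverse events.

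The cost is a few sentences and one derivation. The downside is that Month 24 NODAT follow-up runs about 6 days (734 − 728), at most 28 (756 − 728), past the cut for the other event endpoints. For a subject still on therapy, SAP 8.8 ends the adverse event summary with the analysis window, so a NODAT case after Day 728 may be in the NODAT table but not in that summary. A footnote should say so.
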